Investigator preference for, and confidence in, a specific trial result can be an independent source of post-randomization bias triggering unintended interventions, treatment crossovers, co-intervention bias, and ascertainment bias. The potential for this bias in the ELM trial is minimized by targeting the mindset of the investigators. Their mindset has been shaped by presentations and discussions about objectivity as a hallmark of a scientific mindset, the need for discipline to keep preferences private, and the fallacy of expecting, in advance of a trial result, that one arm will be superior to the other. Trial arms have been renamed with neutral names: Group-Based (the treated group, previously the Eat Love Move (ELM) program); and Self-Directed (the enhanced care comparator). The blind is extended in trial operations to include: blinding to trial hypotheses but not to trial aims among all except the Principal Investigators; blinding to individual level treatment assignment among all but the interventionists; blinding of all but the senior biostatistician to the primary outcome of MetS; and blinding of interventionists to aggregated outcome data completion. Detection of risk of bias resulting from an absence of equipoise will be evaluated on an ongoing basis by assessing crossovers and co-interventions every 3 months, and assessing differential attrition monthly.

ELIGIBILITY

To be eligible for participation, 600 individuals must meet the inclusion criteria and not meet any of the exclusion criteria.

Inclusion Criteria

1. Men and women with MetS, defined by the Joint Interim Statement of the IDF, NHLBI, AHA,WHF, IAS, IASO [1]. To meet these MetS criteria the participant has ≥ 3 of the following 5 components:
 - a. Waist circumference of ≥ 102 cm for men and ≥ 88 cm for women;
 - b. Triglycerides ≥ 150 mg/dL or treatment for elevated triglycerides;
 - c. HDL cholesterol <40 mg/dL in men and <50 mg/dL in women, or treatment for low HDL;
 - d. Systolic blood pressure ≥ 130 mmHg; diastolic blood pressure ≥ 85 mm Hg; or treatment for hypertension;
 - e. Fasting plasma glucose 100-125 mg/dL (range inclusive) or on metformin
2. Age 18 years or older.

Exclusion Criteria

Safety:

3. Unable to walk 2 consecutive blocks without assistance; pain, tightness, or pressure in the chest during physical activity; dizziness or lightheadedness without clearance from their physician.
4. History of an eating disorder in the past 5 years.

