The intervention team at each site consists of a health psychologist, a registered dietitian, and health coach (e.g. lay person who has achieved success with lifestyle modification). Together they co-facilitate group meetings of approximately 15 participants. There is an intensive phase where meetings are held weekly for 3 months and bi-weekly for 3 months. The first 3 months is aimed at initiating change, focusing primarily on food intake, eating behavior, and weight. The last 3 months is aimed at maintenance, focusing on physical activity and a variety of other strategies that enhance maintenance. A maintenance phase follows the intensive phase where participants meet on a monthly basis to check in, report on challenges and successes, and learn about a new topic of their choice.

The format for all of the sessions in the intensive phase is an ecologically valid set of activities within which old habits emerge and new habits can be explored. Participants work out together, prepare a vegetable dish

together, and eat while participating in an experiential exercise. The duration of each session is 90 minutes: physical activity (20 min), cooking demonstration (20 min), and discussion (50 min).

The maintenance phase (months 7 to 24 after randomization) consists of participant-led monthly meetings. Participants are encouraged to broaden their health network by opening maintenance sessions to members of other ELM groups at the site and participating in national ELM activities through the website. Meetings are available at least twice a month for the duration of the intervention to minimize non-attendance due to competing activities. The health psychologist and dietitian alternate in supporting the participant-led meetings.

The Self-Directed Arm

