Vital Status, Adverse Events, Co-Interventions	3, PII, 9, 12, MM, 18, 21, EoT	RA
Contact Info	B,3, PII, 9, 12, MM, 18, 21, EoT	RA
Five-Facet Mindfulness Questionnaire	B, PII, MM, EoT	RA
Eating Competence Questionnaire	B, PII, MM, EoT	RA
Demographics	B, PII, MM, EoT	RA
Labs (Lipid Panel, Glucose and A1c)	B, PII, MM, EoT	RA
Medical History	B, PII, MM, EoT	RA
NCI's Fruit and Vegetable Screener	B, PII, MM, EoT	RA
Food Log and Logistic Plan	B	RA
Perceived Stress Scale	B, PII, MM, EoT	RA
Depression: Patient Health Questionnaire (PHQ-8)	B, PII, MM, EoT	RA
Physical Measures (BP, HR, Waist, Weight, Height)	B, PII, MM, EoT	RA
Automatic Habits: Self-Report Habit Index	B, PII, MM, EoT	RA
Social Support for Diet and Exercise	B, PII, MM, EoT	RA
Sugar-Sweetened Beverage Intake	B, PII, MM, EoT	RA
Visit log	B, PII, MM, EoT	RA
Quality of Life: Short Form Health Survey (SF-36)	B, PII, MM, EoT	RA
Contacts with Health Network	B, PII, MM, EoT	RA
Prescription Medications	B, PII, MM, EoT	RA
MacArthur Ladder of Subjective Social Standing	B	PPT
USDA Food Security	B	RA
Treatment Credibility Questionnaire	B	PPT
Patient Preference for Each Treatment	B	RA
Program Satisfaction	EoT	PPT
Substance Use/Abuse - WHO ASSIST	B	RA

Montreal Cognitive Assessment	B	RA (if needed)
-------------------------------	---	----------------

Change of Status

The trial status of a participant refers to their level of participation in the trial. A *Participant Status Form* is completed whenever a status change occurs. All efforts are made to collect data on the primary outcome (MetS at 2 years), at the very least.

Lost-to-Follow-Up. A participant is considered “lost-to-follow-up” after missing two consecutive trial contacts without responding to messages, texts, or other forms of communication. Staff exhausts all avenues to locate the participant, including telephoning at least 10 times on different days, at varying times of day, contacting secondary contacts and the last medical provider on record, and checking online to identify new contact information. Failure of these attempts triggers a registered letter sent to the participant’s most recent address, to which non-response confirms the status as “lost-to-follow-up.”

Withdrawal from the Intervention. This status applies to a participant who no longer wants to participate in any intervention activities, but is willing to continue completing follow-up visits.

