Withdrawal from the Trial. This status applies to a participant who is no longer willing to participate in any part of the ELM trial, including group meetings, phone calls, or follow-up visits. However, the participant may allow the trial to use lab and medical data routinely collected by his/her provider.

Withdrawal of Consent. This status applies to a participant who no longer wishes to participate in the trial and declines use of data collected during routine visits with the provider. The status must be requested in writing by the participant and reported to the IRB.

Administrative Withdrawal. This status applies to a participant for whom it is no longer safe for the participant or for the trial staff to continue involvement in the trial. The ELM Safety Committee makes this determination in collaboration with the local site PI. This status terminates all further contact with the participant.

Deceased. This status is assigned once confirmed by the safety committee after review of the adverse event.

RETENTION

Retention has been excellent (90-100%) in the past clinical trials administered by the coordinating center at Rush. However, to assume a conservative approach, the sample size is calculated assuming a 20% loss to follow-up at 24 months. Key strategies to enhance retention include: (1) patient-centered recruitment emphasizing consideration of both the pros and cons of participation, from the participant’s perspective; (2) maintaining 2-3 alternative contacts for each participant at enrollment; (3) same staff member assesses outcomes and maintains regular contact with participant over time; (4) minimization of transportation burden by providing free parking and transportation vouchers; (5) reimbursement for assessment time; (6) reminders about appointments for scheduled intervention and follow-up visits; (7) birthday and holiday cards; (8) collaborative partnerships with providers in participating clinics to enhance their support for their patient’s participation; and (9) negotiating with potential drop-outs to encourage partial withdrawal rather than withdrawal of consent. To reduce

differential drop out, all staff are trained and re-trained to insure equipoise, enthusiasm for a conclusive answer to the question rather than a specific result, and timely response to participant inquiries.

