Participants at retention risk, based upon non-attendance at group meetings or inability to contact during 3-month phone calls, triggers a retention protocol. Depending upon the unique situation, the appropriate person (Group-Based interventionist, Self-Directed Coordinator, Outcomes Assessor) makes every effort to contact the participant for the purpose of understanding their perspective and any life situation that may have triggered the retention risk. For participants who are firm about decisions to terminate contact with the trial, every effort is made to keep the door open for a change in this decision at a later time. This is done by requesting the participant's permission to call at a later time to check it, the timing of such a call to be mutually agreed upon.

DATA FLOW

The trial has two main data flows. One is for recruitment and outcome assessment and the other is for intervention support. Data are collected using a variety of electronic systems including:

- **Snap Surveys.** Advanced software that allows for the customization of online data capture forms.
- **SharePoint.** A secure platform that houses the ELM website. SharePoint allows for sharing of data, documents, and publically accessible information.
- **CentrePoint.** A secure platform that transfers accelerometry to the Research Coordinating Unit (RCU).
- **Quantum Portal.** A secure platform that transfers participant lab results directly to the RCU.

Reports provided to investigators feature site-specific aggregated data on recruitment, outcomes, and intervention quality. Research Assistants and interventionists have access to the ELM website, but are limited to viewing only data pertinent to their site and job responsibilities.

Recruitment and Outcome Assessments

Outcomes collection begins at recruitment and continues in 3-month intervals over the 2-year follow-up period. The specific outcome variables collected can be found in the **Outcomes Assessment** section. The RCU provides recruitment reports and data tracking tables, via the ELM website, to help Research Assistants monitor recruitment and submission of outcome measures. **Figure 4** presents the flow of outcomes data.

[figure not shown]

Figure 4. Elm Trial Outcomes Data Flow

Intervention Assessments

The RCU provides delivery support for specific intervention components and reports on the quality of intervention delivery.

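### Retention contacts and visit staffing leave the stated blind unprotected for waist and blood pressure, the two staff-measured components of the primary endpoint

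*Combined protocol and SAP*

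**What the plan says.** **The blind.** Equipoise and Blinding names ascertainment bias as a risk and extends the blind to "blinding to individual level treatment assignment among all but the interventionists". It adds "blinding of all but the senior biostatistician to the primary outcome of MetS". No separate assessor blind is described, but outcome assessors fall under the general statement because they are not interventionists.

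**Retention contacts.** Under Retention: "Participants at retention risk, based upon non-attendance at group meetings or inability to contact during 3-month phone calls, triggers a retention protocol". The response, which is to depend on the circumstances of the case, is that "the appropriate person (Group-Based interventionist, Self-Directed Coordinator, Outcomes Assessor) makes every effort to contact the participant". The contact is meant to bring out how the participant sees matters and what led to the risk.

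**Continuity of staff.** The third listed retention strategy is that the "same staff member assesses outcomes and maintains regular contact with participant over time". Outcomes Assessment (In-Person Follow-Up Visits) likewise wants one person to conduct all of a participant's visits, whenever possible.

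**What that person does.** In Table 2 the row beginning "Physical Measures (BP, HR, Waist, Weight, Height" is assigned to the research assistant (RA) at baseline and all three follow-up visits. The RA also asks about adverse events, co-interventions and contacts with the health network. Of the Group-Based maintenance phase, Interventions says: "Participants are encouraged to broaden their health network by opening maintenance sessions to members of other ELM groups at the site".

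**The concern.** Participants know their arm, because they are told it after randomization. Keeping it from the person who holds the tape and the cuff therefore depends on procedure. The plan states the blind, but elsewhere allows that person into conversations where the arm could easily come out, and sets no rule to prevent it.

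Remission means meeting fewer than 3 of 5 components. Waist is judged at 102 cm (men) or 88 cm (women), and blood pressure at 130/85 mmHg. Near such cut-offs, a small difference in technique can change whether a component counts. If technique differed by arm, the error would be differential. Neither intention-to-treat analysis, the missing-data methods nor a larger sample would remove it.

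**Working it through.** The plan gives no figure on this point to reproduce, so the check is mainly a comparison of sections.

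1. **Who is covered.** The blind exempts only interventionists. The Outcomes Assessor named under Retention is not defined. Table 2 gives outcome measurement to the RA, so taking the two as the same role is a reasonable inference.

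2. **What a retention contact can reveal.** Of the two triggers, missed group meetings exist only in the Group-Based arm, so knowing that trigger means knowing the arm. Missed three-monthly calls can arise in either arm if the trial's common telephone contacts are meant. No rule keeps the assessor away from the first trigger.

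3. **Whether it carries forward.** The two same-staff provisions mean that an assessor who learns the arm at any stage will tend to be the one measuring at 24 months.

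4. **Whether there is a second route.** The RA's interviews are put to everyone, not only to at-risk participants. A truthful answer about health-network contacts may mention group sessions. The content of that instrument is not shown, so this is a possibility only. No visit order places the measurements before the interviews.

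5. **Which components are exposed.** Waist and blood pressure are measured by staff (2 of 5). Triglycerides, HDL and glucose are laboratory values (3 of 5). Four of the five (all but waist) can also be met through treatment, and the RA records prescription medications, so RA-collected information bears on all five. Measurement technique matters for the two.

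6. **Safeguards found.** Hypothesis blinding, neutral arm names, equipoise training, role-limited website access and a common telephone schedule. **Not found:** a non-disclosure instruction, a measurement order, a substitute assessor or an unblinding record.

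7. **Size, as illustration only.** A simulation with assumed component distributions (remission without any lean 7% to 25%) shifted the readings of one whole arm:
   - −1 cm waist and −2 mmHg systolic: 1.0 to 2.0 points of false remission.
   - −2 cm and −3 mmHg: 1.9 to 3.7 points.

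   If only a fraction f of the arm is measured with a lean, and those participants resemble the rest, the bias is about f × the whole-arm value:
   - f = 0.05: 0.05 × 1.0 = 0.05 to 0.05 × 3.7 = 0.19 points.
   - f = 0.20: 0.20 × 1.0 = 0.20 to 0.20 × 3.7 = 0.74 points, the latter being 0.74/20 = 3.7% of the planned 20-point difference (40% against 20%).
   - f = 1: 1.0 to 3.7 points.

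   The documents give neither f nor the size or direction of any lean.

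**The case against.** A reader might infer that these provisions break the blind, or that a site following them cannot keep it. The documents do not support that. The Retention section offers three roles as alternatives, to be chosen by situation. A site could send missed group meetings to the interventionist, Self-Directed participants to their Coordinator, and only missed outcome calls to the assessor. That would satisfy both sections. Nothing says that the assessor is told the trigger or the arm. This objection stands: the text permits the exposure and does not require it.

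A reader might also infer that the assessor blind is the only defence against ascertainment bias. It is not, given the safeguards listed above. An RA who learns the arm but not the hypothesis has less reason to lean either way. These measures reduce the motive for bias, but none stops a participant from disclosing the arm.

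Finally, a reader might set 3.7 points against the planned difference of 20 and conclude that about a fifth of the effect could be artefact. That needs a uniform lean across a whole arm, whereas the retention route reaches only at-risk participants whom the assessor contacts, who disclose, and who still attend at 24 months. The interview route is wider, but its yield is unknown. The distributions behind the simulation are assumed and cannot be checked from the documents. In treated hypertension the component is met whatever the reading, so a lean in blood pressure has no effect there, and whether the simulation allowed for this is not stated.

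Same-staff continuity is also a deliberate retention choice, and taking assessors out of all contact could cost primary-outcome data. The remedy should respect that.

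**Conclusion.** The concern holds as an avoidable risk of unblinding. The retention and staffing provisions leave the stated blind unprotected for waist and blood pressure, and the sections on blinding, retention and visit conduct should be reconciled. This goes beyond wording, because simple changes in conduct would lower the risk in the primary endpoint.

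The size of any bias cannot be derived from the documents. The 1.0 to 3.7 points is at most an illustrative upper range for the leans tried, and not an expected bias. The conclusion rests on two readings: that the Outcomes Assessor is the RA of Table 2, and that the general blinding statement covers that role.

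**What to change.** 1. **Retention.** Have the Research Coordinating Unit, which conducts the randomization, route retention contacts in both arms to staff who already know the arm: the Group-Based interventionist or the Self-Directed Coordinator. Routing has to be central, because a blinded RA cannot sort participants by arm. Limit the assessor to scripted scheduling of missed outcome contacts, so that efforts to obtain the 24-month data continue.

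2. **Outcomes Assessment.** At the post-intensive, mid-maintenance and end-of-treatment visits, complete and enter blood pressure, waist and weight before any interview. Tell participants not to mention their programme to the assessor.

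3. **Visit log.** Record any unblinding of the assessor. Where another RA is already available, have that RA take waist and blood pressure. The documents do not give RA numbers per site, so this should be conditional.

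The cost is a short procedural amendment and a visit-order checklist, with no added assessments, required staff or sample size. The downside is slightly less flexibility over who makes retention calls. Same-staff continuity can otherwise remain.

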With support from the William G. McGowan Charitable Fund, a multidisciplinary team of investigators from the Rush Department of Preventive Medicine developed the Eat Love Move (ELM) Lifestyle Program, a group-based lifestyle intervention for the MetS designed for implementation in the current health care system. Preliminary data suggested that it is plausible that the ELM program can achieve sustained 2-year remission of the MetS in over 50% of patients [10], can be implemented in a clinical setting, and can be delivered with high fidelity at a different national site.

The next step in this progressive program of research is to conduct a multi-site efficacy trial to test whether, and under what conditions, the ELM program can produce a sustained remission of the MetS when delivered across diverse national sites, and whether or not it offers a cost-effective alternative to the best option for lifestyle change that exists in current medical practice and is augmented by widely-available wearable technology.

This multi-site trial is called the Enhanced Lifestyles for the Metabolic Syndrome (ELM) trial. Once the ELM trial began, the ELM Lifestyle Program was renamed the Group-Based Program. It will be compared to enhanced usual care, named the Self-Directed Program. The neutral names for the trial arms preserve equipoise and minimize reactivity to any pre-existing preferences.

SPECIFIC AIMS

The ELM trial aims to compare a Group-Based program to an enhanced usual care comparator called the Self-Directed program when implemented at the national level. A total of 600 participants are recruited from 5 geographic regions (Rochester NY, Wilkes-Barre PA, Chicago IL, Kansas City MO, and Denver CO) and randomized into 1 of the 2 arms in a ratio of 1:1. The primary evaluation will occur after 2 years and will focus on sustained remission of the metabolic syndrome (MetS), sustained change in health behaviors, medical status, quality of life, and the cost-effectiveness of each arm. These aims are operationalized as the following Specific Aims.

PRIMARY AIM 1

Compare the Group-Based and Self-Directed arms on remission of the metabolic syndrome at the 2-year follow-up. The hypothesis is that 2-year remission of the MetS will occur in $\geq 40\%$ in the Group-Based arm and in $\leq 20\%$ in the Self-Directed arm.

SECONDARY AIMS

AIM 2.

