Component 2 (Run-In Period). A Run-In period was developed to identify those who are willing and able to engage in a selected set of activities required by the Group-Based program. This Run-In includes successful completion of the accelerometer protocol (wear accelerometer for 7 consecutive days, 10 hours/day), food and beverage logs (record all food and beverage intake over an entire day for a minimum of 3 weekdays and 1 weekend day), and completion of a worksheet that outlines a logistical plan for how to access vegetables and a location for physical activity (completed at home or during Visit B).

Component 3 (Visit B). The second in-person visit includes a 12-hour fasting blood draw, physical measures, confirmation that the Run-In protocol was completed successfully, and completion of baseline questionnaires. Visit B occurs within 1 month of randomization. At the conclusion of Visit B, prospective participants are asked about continued interest, informed of expected wait time until the start of the program, and entered into the recruitment waiting protocol where they are kept informed of likely dates of starting treatment in ongoing contacts every 2 weeks. If a prospective participant is ineligible based on metabolic syndrome criteria or needs medical clearance for trial participation, the research assistant will follow-up with a phone call.

Randomization

Randomization is conducted by the RCU in permuted blocks and stratified by site. Since 1 of the arms in the trial is a group-based treatment of 15 participants/group, randomization will occur when 30 prospective participants are confirmed to be eligible and interested. Treatment should begin immediately after randomization. Upon randomization, participants are informed of the arm to which they were randomized by a mailed letter, an email, and a follow-up phone call from the respective site interventionist.

As randomization progresses, key population descriptors are compared in the trial arms to ensure that randomization is successfully balancing arms on key baseline characteristics. If any key covariate, such as age, race, gender, employment status, weight, or MetS component, differs by treatment arm, additional stratification in the randomization scheme is considered.

INTERVENTIONS

Highly motivated participants are recruited to help determine the better and more cost-effective way to encourage sustained lifestyle change to reverse the MetS.

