In the Group-Based arm, the RCU supports the intervention by delivering automatic text messages that are tailored to content presented in the prior week and sent on a pre-existing schedule. At selected group meetings, the RCU prepares personalized feedback reports for each participant. The RCU creates reports on intervention progress assessed as class attendance, weight loss compared to the goal of $\geq 5\%$ loss of baseline body weight, and step count compared to the goal of 10,000 steps on most days. The RCU also creates reports on 3 treatment fidelity measures:

- **Delivery.** Documentation of delivery of specific intervention components;
- **Receipt.** Participant self-reports of acquisition and understanding of specific group content;
- **Enactment.** Participant self-reports of daily vegetable intake, mindfulness habits, and old habit recognition.

These reports are uploaded weekly by the RCU to relevant receivers via the ELM website, including interventionists, participants, investigators, and Intervention Coordinating Unit supervisors.

In the Self-Directed arm, data collected by the Self-Directed Coordinator includes completed telephone calls and frequency of participant-initiated contacts. These data are sent to the RCU and displayed quarterly in aggregate form on the ELM website for review by the Self-Directed Coordinator, investigators, and the ICU supervisors.

Participants in both arms are able to view their own data and track their progress in step counts and weight change. The RCU also tracks frequency of daily log-ons to the ELM website by participants in both arms. **Figure 5** presents the flow of intervention data.

[figure not shown]

Figure 5. Intervention Data Flow

SAMPLE SIZE

The primary outcome of the trial is remission of MetS at 24 months. MetS remission (meeting criteria for <3 MetS components) is clinically relevant and the most common endpoint in MetS trials. Sample size was based upon the assumptions that the chi-square test will be used to compare proportions of participants who remit MetS at 24 months by trial arm, with an overall significance level of 0.05, and power of 85%. This requires a sample size of 117 participants per group, or a total sample size of 234.

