The primary hypothesis is achievement of a clinically significant MetS remission at 24 months in $\geq 40\%$ of the participants in the Group-Based program and $\leq 20\%$ of the participants in the Self-Directed program. Achieved rates will be observed, relative to these benchmarks, without statistical support. The primary statistical analysis will compare MetS remission at 24 months between the trial arms using a cluster-adjusted chi-square test. A secondary analysis will compare these rates using a mixed effects logistic regression model examining treatment over time (i.e., baseline through 24 months), a treatment*time interaction, and adjustments for age, gender, race/ethnicity, socioeconomic status, geographic site, BMI, number of co-morbidities, and number of MetS components. Random effects (e.g. random intercept, time, intervention cluster) will be included in the model only if they significantly improve model fit as determined by the likelihood ratio test.

Behavioral treatment targets will be compared by arm, without statistical support, as the proportion of participants achieving clinically significant goals (as presented in the hypothesized pathway in **Figure 3**), based upon the pre-determined benchmarks. Statistical support will be provided by a cluster-adjusted chi-square test. All other secondary and exploratory outcomes will be compared using the relevant cluster-adjusted t-test or chi square test. These comparisons will be conducted using data from post-intensive intervention, mid-maintenance, and end-of-treatment visits and trends over time will be examined. Supplementary analyses will use generalized linear mixed effects modeling, with a behavioral treatment target or weight as the outcome, treatment group as the primary predictor, random effects to account for time, site, and cluster, and selected covariates.

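### Remission reverses the entry rule with no margin, so baseline closeness to the cut-offs predicts it; the primary test ignores this, and the absolute rates include an unknown number of chance crossings

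*Combined protocol and SAP*

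**What the plan says.** - **Entry** (Eligibility, inclusion criterion 1): "To meet these MetS criteria the participant has ≥ 3 of the following 5 components". Drug treatment marks a component as present whatever the reading, for example "diastolic blood pressure ≥ 85 mm Hg; or treatment for hypertension".
- **Baseline reading** (Recruitment and Randomization, Step 3): "The second in-person visit includes a 12-hour fasting blood draw, physical measures". The number of replicate readings is not stated.
- **Primary outcome** (Sample Size): "MetS remission (meeting criteria for <3 MetS components) is clinically relevant and the most common endpoint in MetS trials", assessed at 24 months. The entry cut-offs are the only ones in the document, so it is an inference, though a safe one, that the outcome uses them too.
- **Primary test** (Analysis Plan): "The primary statistical analysis will compare MetS remission at 24 months between the trial arms using a cluster-adjusted chi-square test". Number of MetS components is a covariate in the secondary mixed model only. It is also an exploratory subgroup factor under Aim 4a.
- **Benchmarks** (Analysis Plan): at least 40% in the Group-Based arm and at most 20% in the Self-Directed arm. "Achieved rates will be observed, relative to these benchmarks, without statistical support".
- **Projections** (Analysis Plan, health economic paragraphs): the observed remission rate is combined with national estimates to project disease cases averted and savings.

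**The concern.** When people are selected because a reading lies above a line and are later scored against the same line, some fall below it with no real change. A participant with exactly three components whose triglycerides read 152 mg/dL at baseline and 148 mg/dL at 24 months has remitted under this definition, provided the other components do not change. A participant with five components, or with components held present by treatment, can hardly do so by chance.

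Two things follow. First, component count, component values and treatment status at baseline are strong predictors of the primary outcome. All are collected, and the primary test uses none of them. Second, each arm's remission rate mixes real change with chance crossing. That matters where the rate is read on its own: against 40% and 20%, and in the dissemination projections. Chance crossing can also shrink the between-arm difference, which is the denominator of the cost-effectiveness ratio.

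**Working it through.** **1. The plan's own figure.** Take 40% vs 20%, two-sided 0.05, 85% power and 20% loss (the loss is given under Retention):

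n = [1.960·√(2·0.30·0.70) + 1.036·√(0.24 + 0.16)]² / 0.20² = (1.270 + 0.655)² / 0.04 ≈ 92.7, so 93 per arm; 93/0.80 = 116.25, so 117.

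This reproduces the stated 117 per group. The 40% and 20% therefore enter as rates observed on this endpoint, with any chance crossings already inside them.

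**2. Crossing with no true change.** The documents give no within-person variability, component prevalence or treated fraction. Every input below is an assumption.

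*Model A, physical units.* Within-person SDs: waist 2 cm, triglycerides 20%, HDL 7.5%, systolic 8 and diastolic 5.5 mmHg, glucose 5%. Half are treated for blood pressure, and treatment does not change. Participants are selected on one visit with at least 3 components and glucose below 126, then read again independently.

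- Central case: 12.3% remit. By baseline count of 3, 4 and 5: 21%, 5% and 1%.
- Noise scaled by 0.5 to 1.25, with lighter or heavier treatment: 4.7% to 15.8%.
- Rebuilt with different between-person spreads: 12.0% centrally, range 3.4–15.3%.

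*Model B, standardized scale.* Prevalences 0.95, 0.55, 0.50, 0.60 and 0.60 for criteria a to e; correlation between components 0 to 0.4. Heavy treatment means treated fractions of 0, 0.25, 0.10, 0.65 and 0.15.

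| Retest reliability (a to e) | No treatment | Heavy treatment |
|---|---|---|
| 0.99, 0.90, 0.95, 0.90, 0.90 | 8.6–9.5% | 3.8–4.3% |
| 0.98, 0.80, 0.90, 0.80, 0.80 | 11.4–12.5% | 5.0–5.5% |
| 0.97, 0.65, 0.85, 0.65, 0.65 | 14.0–15.4% | 6.1–6.8% |

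A wider set of 36 scenarios, with reliability from 0.50 to 0.99 and three prevalence sets, gave 4.0% to 39.3%; 14 of them exceeded 16%. In all 36, participants entering with exactly three components made up 68–91% of those who crossed.

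**3. What adjustment is worth.** In the simulations, adjusting for count cut the individual-level variance of the risk difference by 8–14%. Adding component values and treatment status cut it by 18–27%. Only the individual-level part of the variance can shrink in this way. With 300 × 0.8 = 240 evaluable per arm and 15 × 0.8 = 12 per group, its share of the total is:

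- ICC 0.15: (0.16 + 0.24·0.85) / (0.16 + 0.24·2.65) = 0.364/0.796 = 46%
- ICC 0.01: (0.16 + 0.24·0.99) / (0.16 + 0.24·1.11) = 0.398/0.426 = 93%

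Here 2.65 = 1 + 11·0.15 and 1.11 = 1 + 11·0.01. Multiplying through:

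| Adjustment | ICC 0.15 | ICC 0.01 |
|---|---|---|
| Count | 4–6% | 7–13% |
| Count, values, treatment | 8–12% | 17–25% |

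**4. A margin rule, for comparison.** Suppose a component counts as resolved only if it clears its cut-off by one within-person SD. In Model A the no-change rate falls from 12.3% to 3.8%. With true shifts calibrated to crude rates of 20% and 40%, the rates become 7.4% and 20.6%.

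**The case against.** **No inferential harm.** Assessors are blinded to assignment, so chance crossing should be about equal in the two arms. It creates no false difference and does not inflate type I error. This stands in full. A reader might infer a loss of power: if 40% and 20% were true rates with a floor of 5% or 16% added among non-remitters, they would become 43.0% vs 24.0% or 49.6% vs 32.8%, and power at 94 evaluable per arm, ignoring clustering, would fall from 85% to 79% or 65%. The plan does not use the rates that way, so its calculation is unaffected.

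**The size is guesswork.** Largely right. The recruitment section describes earlier screens, a records search for probable MetS and self-reported components by telephone, which the models omit. Requiring one earlier independent qualifying reading cut the central figure in a similar simulation from 13% to 8%, and a 7–16% range to 4–11%. This is an upper illustration of that effect, since self-report is imprecise and not everyone comes through records. Newly started treatment and true worsening also offset chance crossing. The Background cites 11.1% two-year remission in the lifestyle arm of a US diabetes prevention trial, below the 12% central no-change figure. That comparison is not decisive, because the definition there may differ.

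**Much is already planned.** Count is a covariate in the secondary model and a forest-plot subgroup, and MetS components and severity are secondary outcomes. This stands, and it limits what needs adding. It does not bring the information into the primary contrast or put it beside the benchmarks.

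**A margin is arbitrary.** It removes 12.3 − 3.8 = 8.5 points with no effect, but 40 − 20.6 = 19.4 points from an arm at 40%, and it shrinks the difference from 20 to 20.6 − 7.4 = 13.2 points. An arm exactly at 40% would fail by construction. This stands.

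**Conclusion.** The structure is certain from the text, allowing for the inference on cut-offs: the outcome reverses the entry rule with no margin, and the primary test uses no baseline covariates. That chance crossers come mainly from participants entering with three components held in every scenario run. Their number is unknown: roughly 4–16% under the assumed inputs, and higher under less reliable measurement.

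The practical consequence is moderate. The primary comparison is valid but gives up precision that costs almost nothing to recover, and the absolute rates need to be read with baseline count in view. The variance gains also rest on assumed inputs.

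A reader might go further and conclude that a known share of participants will remit by noise, or that chance uses up most of the Self-Directed arm's 20%. The documents do not support either: they contain no variability data, and the result moves several-fold with the inputs. Nor do they support replacing the endpoint, or withholding the term clinically significant unless a margin is cleared.

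**What to change.** In the Analysis Plan, in the paragraph on the primary hypothesis:

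1. Keep fewer than 3 components at 24 months as the primary endpoint.
2. Estimate the primary contrast as a cluster-adjusted, covariate-standardized risk difference. Adjust for baseline number of components (3, 4, 5), baseline component values and baseline treatment status. Coding waist and HDL as distance from the sex-specific cut-off makes closeness explicit. Fix the covariate list before outcomes are examined by arm.
3. Report the rates compared with 40% and 20% separately for participants entering with 3 and with 4–5 components, beside the overall rates.
4. Optionally, add a margin-based scoring as a sensitivity analysis of the between-arm difference only. Do not judge the benchmarks, or the term clinically significant, by it.

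Cost: slightly more programming and a pre-specified covariate list. Table 2 already schedules labs, physical measures and prescription medications at baseline and end of treatment, so no visits or participants are added.
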